4.4. Part 2 (Optional OLE)

4.4.1. Criteria for Withdrawal of Participants in Part 2

A participant may be discontinued from Part 2 of the study (including study drug and all assessments) at any time if the participant or the investigator feels that it is not in the participant's best interest to continue. The following is a list of possible reasons for Part 2 study discontinuation:

1. Long-term placement in a skilled nursing convalescent home, or long-term care facility at screening and requires continuous nursing care. (i.e., >3 months)
2. If, in the opinion of the investigator and Alector, they are unable to follow protocol procedures

3. If they develop intercurrent illness that would confound the interpretation of safety and efficacy data
4. CDR® plus NACC FTLD global score >2 during Part 2
5. AL001 is commercially available in the country where the participant is being treated
6. Participant withdrawal of consent
7. Lost to follow-up
8. Discretion of the investigator
9. Administrative or other reasons (e.g., premature termination of the study by Alector)
10. Participant is noncompliant with the protocol
11. Participant has a serious or intolerable AE that, in the investigator's opinion, requires withdrawal from the study drug
12. Serum aminotransferase levels (ALT or AST) $>3 \times$ ULN AND total bilirubin $>2 \times$ ULN without an alternative explanation
13. Anaphylaxis
14. Infusion-related or injection-related reaction despite adequate premedication for an initial occurrence of a moderate to severe infusion-related reaction ([Section 5.1.2](#)) or if the participant experiences any of the following events: mucosal tissue involvement, airway compromise, or symptomatic hypotension with systolic blood pressure <90 mm Hg measured in the supine position
15. Occurrence of an intercurrent illness that, in the investigator's opinion, will affect assessments of clinical status or safety to a significant degree
16. Use of a nonpermitted concomitant medication per [Section 4.1.2](#) (as appropriate)
17. Pregnancy

All Part 2 participants who discontinue the study drug and/or all assessments prior to the scheduled Week 197 visit should be encouraged to return to the site for a Part 2 EOS visit. Part 2 EOS assessments should be completed as soon as possible after the decision is made. A Safety Follow-Up visit will be performed 10 weeks after the participant's last study drug administration. Reasonable attempts will be made by the investigator to obtain reasons for participant withdrawals (e.g., 2 documented telephone calls on different days, followed by 1 registered letter). The reason for the participant's withdrawal from the study will be specified in the participant's source documents and in the eCRF.

4.5. Replacements (Part 1 Only)

Participants who do not meet all eligibility criteria at screening or who qualify at screening but are not enrolled within the screening period may be reconsented, assigned a new screening number, and rescreened (see [Section 6.2](#)).

Participants who withdraw from the study may be replaced at the discretion of Alector and in consultation with the investigator.

Note: the optional OLE (Part 2 of the study) is open to any eligible participant from Part 1; thus, replacing participants who leave the OLE is not applicable.

5. STUDY TREATMENTS

This is an open-label study; all participants will receive AL001 (Part 1 treatment period and Part 2 optional OLE).

Each participant who provides informed consent will be assigned a screening number that uniquely identifies the participant. It is the responsibility of the investigator to ensure each participant is eligible for the study prior to enrollment. Participants who complete Part 1 will retain their unique screening number if they participate in Part 2. Alector will maintain a central screening log and utilize an electronic data capture (EDC) and Interactive Response Technology (IRT) systems to implement enrollment, to assess current inventories of AL001, to initiate necessary resupply of drug and to document discontinuation of drug.

5.1. Treatments Administered

Part 1(Treatment Period)

All participants will receive AL001 (60 mg/kg IV) on Day 1, and then q4w for a total of 25 doses over a 96-week period.

Part 2 (Optional OLE)

Participants in the OLE will receive AL001 60 mg/kg IV q4w. An individual participant may continue to receive AL001 on the OLE portion of the study for up to 25 doses over a 96-week dosing period, or until commercial availability of AL001 in the country where the participant is being treated, whichever is earlier.

5.1.1. Administration Instructions

AL001 will be administered intravenously over approximately 60 minutes at the investigational site by study-trained clinic staff under the supervision of the investigator or their designee, or by a home health service, as applicable (See [Appendix 3](#)). Dosing solution preparation instructions will be provided separately in a Pharmacy Manual.

Documentation of study drug administration will be recorded in the source documentation and documented in the eCRF.

The investigator is responsible for the education of study staff in the correct administration of the study drug.

Participants will be monitored for at least 60 minutes after the end of infusion ([Section 5.1.2](#)) and completion of all activities scheduled for that visit day and discharged at the discretion of the investigator.

5.1.2. Infusion-Related and Injection-Related Reactions

All participants will be monitored for infusion-related reactions or injection-related reactions during the infusion/injection and immediately afterwards for at least 60 minutes.

Injection-related reactions can be localized at the site of the injection or systemic and should be treated per institutional guidelines. If a participant experiences a mild infusion-related reaction,

the infusion should be halted. Once the reaction has resolved, the infusion rate will be resumed at half the most recently used rate (e.g., from 60 mL/hr [1.0 mL/min] to 30 mL/hr [0.5 mL/min]). The infusion should be stopped immediately for any participant who experiences a moderate to severe infusion-related reaction (e.g., fever or chills), and the participant should receive aggressive symptomatic treatment. The infusion should not be restarted before all symptoms have disappeared, and then it should be restarted at half of the initial rate. The infusion should not be resumed if there is a second occurrence or if the participant experiences any of the following events: mucosal tissue involvement, airway compromise, or symptomatic hypotension with systolic blood pressure <90 mm Hg measured in the supine position.

In addition, in the event of an infusion-related reaction, a sample of blood should be obtained for PK serum and ADA assessment of AL001, and testing should be performed for C-reactive protein, tryptase, and Interleukin 6 (IL-6). Further details regarding infusion-related reactions are provided in the IB.

5.2. Identity of Investigational Product

5.2.1. Study Drug Formulation

The study drug (AL001) is provided as a liquid solution formulated at a concentration of 50 mg/mL in an aqueous solution containing AL001 (human recombinant anti-human Sortilin IgG1 monoclonal antibody) in 20 mM histidine / histidine HCL, 7.5% (w/v) sucrose and 0.02% (w/v) polysorbate-80 at pH 5.5.

5.2.2. Study Drug Packaging and Labeling

The container closure system for AL001 study drug consists of a 20R Type I (EP-compliant) clear glass vial, with a coated bromobutyl rubber stopper and an aluminum crimp seal with blue flip-off cap. Each single-use vial will contain at least █ mL of a █ mg/mL solution of AL001 study drug.

AL001 will be labeled to meet applicable requirements of the Food and Drug Administration (FDA) as well as the EU Guideline for Good Manufacturing Practice for Investigational Medicinal Products (Annex 13), and other local requirements.

5.3. Management of Clinical Supplies

Specific instructions about the storage, preparation, and administration of AL001 are provided in the Pharmacy Manual. Additional information about AL001 is provided in the IB and on the Certificate of Analysis.

5.3.1. Study Drug Supply

Alector will supply AL001 to the investigational sites, as detailed in the Pharmacy Manual.

5.3.2. Study Drug Storage

Study drug will be shipped at a temperature of 2°C to 8°C.

Upon receipt at the investigational site, the study drug shall be stored securely under controlled conditions until use, in a refrigerator, set to maintain 2°C to 8°C. From preparation of dosing solution to administration at the investigational site, dosing solution storage time will be limited to 4 hours at ambient temperature and no more than 24 hours at 2°C to 8°C.

The investigators will be fully responsible for the security, accessibility, and storage of the study drug while they are at their investigational facility.

5.3.3. Study Drug Accountability

The investigational site will maintain accurate records of receipt of all study drug, including dates and condition of receipt. In addition, accurate records will be kept (including the initials of the person dispensing the study drug) regarding when and how much study drug is dispensed and used by each participant in the study. Reasons for departure from the expected dispensing regimen must also be recorded. At the completion of the study, to satisfy regulatory requirements regarding drug accountability, all study drug will be reconciled and retained or destroyed according to applicable regulations.

5.3.4. Study Drug Return or Disposal

Study product supplies, including partially used or empty vials, should be disposed of at the site per local standard operating procedures. If study product supplies cannot be destroyed on-site, they may be shipped back to the return depot. Please see Pharmacy Manual for additional instructions.

5.4. Misuse for Illegal Uses

AL001 is supplied for use only in this clinical study and should not be used for any other purpose.

5.5. Blinding

This is an open-label study where all participants will receive AL001, and doses are not concealed; blinding, therefore, is not required.

5.6. Prior and Concomitant Therapy

All concomitant medications used by a participant from informed consent through the Part 1/Part 2 EOS or Safety Follow-up visit, whichever is later, will be recorded in the participant's eCRF and coded using the World Health Organization Drug Dictionary (WHO-DD), March 2019 or later. The minimum requirement is that drug name, total daily dose, route, frequency of dosing, indicated use, and the dates of administration are to be recorded. This will include all prescription drugs, herbal products, vitamins, minerals, vaccines, topical medications, and over-the-counter medications. Any changes in concomitant medications also will be recorded in the participant's eCRF.

During the course of the study, participants are anticipated to continue the use of accepted prescribed medications identified during the screening procedures, in accordance with study

inclusion and exclusion criteria. Participants should be advised against taking any new medication, both prescribed or over-the-counter, without consulting the investigator, unless the new medication is required for emergency use.

Any concomitant medication deemed necessary for the welfare of the participant during the study may be given at the discretion of the investigator. However, it is the responsibility of the investigator to ensure that details regarding the medication are recorded in full in the eCRF.

Any restricted medication must have been stopped as required by the study inclusion and exclusion criterion ([Section 4.1.1](#) and [Section 4.1.2](#), respectively); participants who start these medications during the study may be withdrawn from study drug at the discretion of the Medical Monitor.

6. STUDY ASSESSMENTS AND PROCEDURES

Before performing any study procedures, all potential participants and study partners will sign an informed consent form (ICF). If the study participant is not competent, a legally authorized representative must provide informed consent on their behalf, and the participant must provide assent, in accordance with the local regulations, guidelines, and IRB/IEC. Participants and study partners will have the opportunity to have any questions answered before signing the ICF. The investigator must address all questions raised by the participants. The investigator or designee will also sign the ICF. Further details of informed consent are provided in [Section 10.3](#).

Timing and frequency of all assessments and procedures for Part 1 are presented in the Schedules of Assessments ([Table 4](#),[Table 5](#)) and Schedule of PK, Immunogenicity, and PD Biomarker Sample and Imaging Assessments ([Table 6](#)). Timing and frequency of all assessments and procedures for Part 2 are presented in the Schedules of Assessments ([Table 7](#) and [Table 8](#)) and Schedule of PK, Immunogenicity, and PD Biomarker Sample and Imaging Assessments ([Table 9](#)). Asymptomatic participants require the study partner at the COA visits only; symptomatic participants require the study partner at each visit.

Adaptations to visits and procedures under the exceptional circumstance of COVID-19 pandemic are detailed in [Appendix 3](#).

6.1. Timing of Study Drug Administration

Pre-dose Study Procedures and Assessments:

- Perform COAs prior to any potentially stressful procedure (e.g., blood collections, lumbar punctures, imaging)
- PE, or limited or symptom-directed examination
- Neurological examination, or limited or symptom-directed examination
- Vital signs and weight, including blood pressure (BP), pulse, body temperature, and respiratory rate
- Triplicate 12-lead ECG
- Obtain blood and urine samples for chemistry, hematology, coagulation, serology, pregnancy testing, and urinalysis.
- Obtain blood samples for ADAs
- Obtain blood samples for PK and PD
- Obtain blood sample for whole genome sequencing (WGS) (Part 1 only)
- Collect CSF samples via lumbar puncture for PK and PD (Part 1 only)
- Perform MRI
- Perform Sheehan Suicidality Tracking Scale (Sheehan-STS)
- Review of concomitant medication(s)

- Record any AEs and SAEs

Dosing Procedures:

- AL001 will be administered to participants per institutional practice ([Section 5.1](#)).

Post-dose Procedures:

- Obtain serum samples for PK
- Triplicate 12-lead ECG
- Vital signs, including BP, pulse, body temperature, and respiratory rate
- Review of concomitant medication(s)
- Record any AEs and SAEs

6.2. Rescreening Criteria

Part 1 participants who are not enrolled within the screening period will be screen failed. Rescreening may be allowed after approval from the Medical Monitor. Participants who rescreen after the screening period must be reconsented with a new screening number, and the screening assessments must be repeated. The participant may not be required to repeat the MRI imaging or CSF screening assessment, if performed within 3 months prior to screening. Clinical outcome assessments performed within 8 weeks prior to screening may not be required to be repeated after approval from the Medical Monitor.

Those aFTD-GRN and FTD-GRN participants who have completed Study AL001-1 (described in [Section 1.2.2](#)) may enroll in this study. Participants must be rescreened after completion of Study AL001-1 and meet all inclusion/exclusion criteria applicable to this study. The participant may not be required to repeat the imaging (MRI) or CSF baseline assessment if performed within 3 months prior to screening. The participant may not be required to repeat the safety and tolerability assessments, if performed within 6 weeks prior to screening.

All participants are not required to report WGS results, and there is no time restriction for reporting.

Rescreening is not applicable for Part 2 of the study.

6.3. Sample Collections

Specific information on clinical laboratory, ADAs, PK, PD, exploratory PD biomarker, and WGS sample collection, processing, storage, and shipment will be provided in separate manuals.

Unused portions of PK, PD, and/or exploratory PD biomarker samples remaining after all applicable protocol-defined tests have been performed may be retained and maintained, for up to 10 years, if the participant agrees and provides consent separately as described in [Section 10.3](#). These samples may be used for future testing not described in this protocol.

For participants who have provided consent, the samples may be used for testing including the following: further evaluation of PD biomarkers (e.g., associated with efficacy, AEs, or disease

progression), further clarification or characterization of the disease, further evaluation of the study drug's effects, and/or development of assays (e.g., PD biomarker or diagnostic assays).

6.4. Cerebrospinal Fluid Sampling

Cerebrospinal fluid samples will be collected in Part 1 only via lumbar puncture prior to study drug administration (if applicable) at Screening, Week 25, Week 49, and Week 97 (or the Part 1 EOT/EOS Visit) to evaluate PK, PD, and exploratory PD biomarker measures. The Week 25 lumbar puncture may be adjusted as determined by Alector's review of exploratory PD biomarkers.

Specific information on the collection, processing, storage, and shipment of CSF samples will be provided in a separate manual.

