3.2. Study Duration

Part 1 (Treatment Period):

- A screening period (within 6 weeks prior to Day 1).
- A treatment period (96 weeks, Day 1 through Week 97).
- Participants who discontinue study drug prior to completing the 96-week Part 1 treatment period should be encouraged to complete all remaining scheduled assessment visits through Part 1 (including COAs, MRI, and CSF evaluations).
 - A Part 1 End of Treatment (EOT) visit will be completed by participants who discontinue study drug but remain in the study and continue to perform assessments. Part 1 EOT assessments should be completed as soon as possible after the decision is made. A Safety Follow-Up visit will be performed 10 weeks after their last study drug administration. The Safety Follow-up visit may be substituted by a scheduled visit if it occurs within the same window.
 - A Part 1 End of Study (EOS) visit will be completed by participants who discontinue study drug and all assessments. Part 1 EOS assessments should be completed as soon as possible after the decision is made. A Safety Follow-Up visit will be performed 10 weeks after their last study drug administration.
- At Week 97, participants who complete the Part 1 96-week treatment period will have the option to continue to receive AL001 in Part 2 (OLE) of the study.
 - Participants who do not continue in Part 2 will complete a Part 1 EOS visit at the scheduled Week 97 timepoint. A Safety Follow-up visit will be performed 10-weeks after their last study drug administration.
 - Participants who continue in Part 2 will complete the Week 97 visit and continue to Part 2 (Week 101).

Part 2 (Open-Label Extension)

- OLE eligibility confirmation (prior to Week 101 study drug administration).
- A treatment period (96 weeks, Day 101 through Week 197), or until AL001 is commercially available in the country where the participant is being treated, whichever is earlier.
- Participants who discontinue study drug and/or all assessments prior to completing the 96-week Part 2 treatment period will complete a Part 2 EOS visit as soon as possible after the decision is made. A Safety Follow-Up visit will be performed 10 weeks after their last study drug administration.
- At Week 197, participants who complete the Part 2 96-week OLE period will complete a Part 2 EOS visit at the scheduled Week 197 timepoint. A Safety Follow-up visit will be performed 10-weeks after their last study drug administration.

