6.10. Unscheduled Visits

Unscheduled visits may occur at any time while the participant is enrolled in the study.

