6.11. Part 1 End of Treatment Visit

Participants who discontinue study drug prior to completing the 96-week Part 1 treatment period should be encouraged to complete all remaining scheduled assessment visits through Part 1 (including COAs, MRI, and CSF evaluations).

A Part 1 EOT visit will only be completed by participants who discontinue study drug but remain in Part 1 of the study and continue to perform all assessments ([Section 4.3.1.1](#)). Part 1 EOT assessments should be completed as soon as possible after the decision is made.

The EOT visit may be substituted by a scheduled study visit if it occurs within the same window.

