6.12. End of Study Visit

6.12.1. Part 1 End of Study Visit

Participants who discontinue study drug and all assessments prior to completing the 96-week Part 1 treatment period ([Section 4.3.2](#)) will complete a Part 1 EOS visit as soon as possible after the decision is made. The Part 1 EOS visit may be substituted by a scheduled study visit if it occurs within the same window.

Participants who complete the 96-week Part 1 treatment period, at Week 97, will have the option to continue to receive AL001 in Part 2 (OLE) of the study. Participants who do not continue in Part 2 will complete a Part 1 EOS visit at the scheduled Week 97 timepoint. Participants who continue in Part 2 will complete the Week 97 visit and continue to Part 2 (Week 101).

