- ^d A complete neurological examination will be performed at screening, Week 25, Week 49, Week 73, Week 97 and at EOT/EOS/Safety Follow-up, and includes the evaluation of consciousness, orientation, cranial nerves, motor and sensory system, coordination and gait, and reflexes. Limited or symptom-directed examinations are required at all other specified time points, prior to study drug administration (if applicable). A limited examination or symptom-directed examination should focus on the affected organ system or body area. Record abnormalities observed at screening on the General Medical History and Baseline Conditions page of the eCRF. At subsequent visits, record new or worsened clinically significant abnormalities as AEs on the AE eCRF.
- ^e Vital signs will be recorded after the participant has been resting for at least 5 minutes in the supine position. On dosing days, vital signs will be recorded prior to infusion (pre-dose) and within 15 minutes after the end of infusion, and once at all other specified time points as indicated. Weight (kg) will be collected at the same visits that vital signs are taken.
- ^f Triplicate 12-lead ECGs will be obtained after the participant has been in the supine position for ≥ 5 minutes. On specified dosing days ECG will be obtained prior to study drug administration and within 60 minutes after the end of infusion, and once at all other specified time points as indicated. Additional ECG monitoring must be performed during the treatment period if clinically indicated.
- ^g Details on timing of vital signs, serum PK samples, triplicate ECGs, serum ADA samples, progranulin plasma samples, exploratory plasma PD biomarker samples, whole blood samples for WBC analysis, and exploratory whole blood PD biomarker samples are provided in [Table 6](#).
- ^h Samples will be collected prior to study drug administration (if applicable).
- ⁱ If the lumbar puncture is moved to a different visit, the coagulation panel will be moved to the visit immediately preceding the new lumbar puncture visit.
- ^j All women of childbearing potential will have a serum pregnancy test at screening. Urine pregnancy tests will be performed at specified subsequent visits. If a urine pregnancy test is positive, it must be confirmed by a serum pregnancy test.

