6.2. Clinical Laboratory Evaluations

Blood and urine samples that will be collected for clinical safety laboratory tests (chemistry, coagulation, hematology, urinalysis, serology, and pregnancy testing) are indicated in [Table 8-1](#).

Laboratory assessment analysis will be performed at a central laboratory, with the exception of urine pregnancy testing which will be done at local laboratories.

Hematology, coagulation, serum chemistry, and urinalysis will be performed at the timepoints identified in [Appendix 14.1](#), [Appendix 14.2](#), [Appendix 14.4](#) and [Appendix 14.5](#). Additionally, unscheduled testing may be done during the study if medically indicated.

Abnormal clinical laboratory values will be flagged as either high or low (or normal or abnormal) based on the reference ranges for each laboratory parameter. The investigator will determine whether any of the abnormally high or low results are clinically significant or not clinically significant. Any clinically significant results will be entered into the eCRF as AEs, however the attribution of clinical significance will not be available in the data.

Actual results and change from baseline values for hematology, coagulation, serum chemistry, and urinalysis tests will be summarized by visit using descriptive statistics.

Shift from baseline in hematology, coagulation, serum chemistry, and urinalysis tests results relative to the reference range will be summarized by visit using the frequency count and percentage of participants in each category.

Refer to Section 4 for the definition of baseline.

All laboratory test results will be presented in data listings.

Table 8-1 Laboratory Assessments

Chemistry	Coagulation	Hematology	Serology
Total bilirubin	PT	HbA1c	anti-HCV
Direct bilirubin	INR	Leukocytes	anti-HIV
Alkaline phosphatase	aPTT	Erythrocytes	HIV antigen
gammaGT		Hemoglobin	HBsAg
AST		Hematocrit	Total hepatitis B core antibody
ALT		Thrombocytes (platelets)	
LDH		MCV	
Creatine kinase		MCH	
Creatinine ^a		MCHC	
Urea			
Uric acid			
Cholesterol			
HDL			
LDL			
Triglycerides			
Total protein			
Albumin			
Glucose			
Bicarbonate			
Inorganic phosphate			
Sodium			
Potassium			
Calcium			
Chloride			
Magnesium			
Lipase			
Apolipoprotein B100			
	Urinalysis		Pregnancy Test
	Hemoglobin (blood urine)		Serum β-hCG or urine pregnancy test ^c
	Ketones		
	Glucose		
	Protein		
	Leukocyte esterase		
	Nitrite		
	pH		
	Specific gravity		

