f Triplicate 12-lead ECGs will be obtained after the participant has been in the supine position for ≥ 5 minutes. On specified dosing days ECG will be obtained prior to study drug administration and within 60 minutes after the end of infusion, and once at all other specified time points as indicated. Additional ECG monitoring must be performed during the treatment period if clinically indicated.

g Details on timing of vital signs, serum PK samples, triplicate ECGs, serum ADA samples, progranulin plasma samples, exploratory plasma PD biomarker samples, whole blood samples for WBC analysis, and exploratory whole blood PD biomarker samples are provided in protocol Table 6. H Samples will be collected prior to study drug administration (if applicable).

I If the lumbar puncture is moved to a different visit, the coagulation panel will be moved to the visit immediately preceding the new lumbar puncture visit.

J All women of childbearing potential will have a serum pregnancy test at screening. Urine pregnancy tests will be performed at specified subsequent visits. If a urine pregnancy test is positive, it must be confirmed by a serum pregnancy test.

K Blood serum samples will be collected for determination of ADA prior to study drug administration (if applicable). Additional ADA samples should be collected in participants with signs and symptoms of infusion-related reactions. A sample of blood should be obtained for PK serum and ADA assessment of AL001, and testing should be performed for C-reactive protein, tryptase, and Interleukin 6 (IL-6).

L Cerebrospinal fluid samples will be collected via lumbar puncture prior to study drug administration (if applicable). The timing of lumbar puncture may be adjusted as determined by Alector's review of exploratory PD biomarkers. GRN mutation carriers previously treated in Study AL001-1 may not be required to repeat the CSF assessment if it has been performed within 3 months prior to screening.

M If the assessment is unable to be performed at the scheduled visit due to the COVID-19 pandemic, the assessments may be performed at a future on-site visit with approval from the medical monitor. Refer to protocol Appendix 3 for additional details on trial adaptations due to COVID-19.

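### The early-stop lumbar puncture at the Part 1 EOT/EOS visit has no coagulation panel scheduled for it; for stops before Week 45 the newest scheduled panel can be up to 24 to 26 weeks old, against about 4 weeks at scheduled punctures

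*Protocol*

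**What the plan says.** Protocol section 6.4 collects CSF in Part 1 at "Screening, Week 25, Week 49, and Week 97 (or the Part 1 EOT/EOS Visit". For someone who stops study drug early but stays in the study, section 3.2 states that "Part 1 EOT assessments should be completed as soon as possible after the decision is made". It sets the same timing for the EOS visit of someone who leaves altogether.

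Coagulation (PT, INR, aPTT) has its own row in the schedules, separate from chemistry and hematology. Table 4 marks it at screening, Week 21 and Week 45. The continuation schedules, protocol Table 5 and SAP 14.2, show a late panel one column before the first of their two puncture marks, and the SAP copy shows one more mark near Week 73. Neither shows a coagulation mark at EOT/EOS.

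The linking rule is a footnote (h in protocol Table 4, i in Table 5). For a puncture moved to another visit, "the coagulation panel will be moved to the visit immediately preceding the new lumbar puncture visit". SAP 14.2 carries the same rule: "If the lumbar puncture is moved to a different visit, the coagulation panel will be moved".

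Some flexibility exists. Protocol 6.11 says "The EOT visit may be substituted by a scheduled study visit if it occurs within the same window", and 6.12.1 gives the EOS visit the same option. Protocol 6.10 says "Unscheduled visits may occur at any time while the participant is enrolled in the study", and SAP 6.2 says "Additionally, unscheduled testing may be done during the study if medically indicated". Completers are covered separately by 6.12.1: "Participants who do not continue in Part 2 will complete a Part 1 EOS visit at the scheduled Week 97 timepoint".

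**The concern.** The protocol pairs each scheduled post-baseline puncture with a recent coagulation panel and has a rule to keep the pair together if the puncture moves. The EOT/EOS puncture falls outside that arrangement. It is triggered by a decision to stop, and by then the preceding visit has usually taken place without a panel.

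Exclusion 14 names coagulopathy, anticoagulation and thrombocytopenia among the contraindications to puncture, but it is applied at entry. No later puncture is formally conditional on it. What sets EOT/EOS apart is that the recent panel is missing too.

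The reasons for stopping are not unrelated to bleeding risk. Section 4.3.1.1 lists combined aminotransferase and bilirubin elevation, for which PT/INR is directly relevant, and use of a prohibited medication. Anticoagulants are on the prohibited list (exclusion 27). Some early stoppers may therefore have a coagulation status that has changed since their last panel. At stake is the safety of a research procedure in people leaving treatment. The primary analysis is not affected.

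**Working it through.** **Inputs.** Table 4 and Table 5 give these study days: Week 17 = 113, Week 21 = 141, Week 25 = 169, Week 41 = 281, Week 45 = 309, Week 49 = 337, Week 65 = 449, Week 69 = 477, Week 73 = 505, Week 93 = 645, Week 97 = 673. They follow day = 7 × (week − 1) + 1; for Week 21, 7 × 20 + 1 = 141. Screening may fall up to 42 days before Day 1. The documents state no panel age, so there is no figure of the plan's own to reproduce.

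**Formula.** Panel age in weeks = (puncture day − day of newest scheduled panel) / 7.

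**Scheduled punctures.**
- Week 25, panel at Week 21: (169 − 141)/7 = 4
- Week 49, panel at Week 45: (337 − 309)/7 = 4
- Week 97, late panel read as Week 93: (673 − 645)/7 = 4

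With both visits at the edge of their ±7-day windows, the range is 2 to 6 weeks.

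**EOT/EOS puncture, longest age of the newest scheduled panel.**
- Stop before Week 21 (screening panel): (141 − 1 + 42)/7 = 26
- Stop between Weeks 21 and 45 (Week 21 panel): (309 − 141)/7 = 24

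These are 26/4 = 6.5 and 24/4 = 6 times the scheduled interval.

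**Examples.**
- Stop at Week 17: (113 − 1)/7 = 16 weeks, up to (113 − 1 + 42)/7 = 22
- Stop at Week 41: (281 − 141)/7 = 20 weeks
- Stop at Week 65: (449 − 309)/7 = 20 weeks, whichever way the later coagulation row is read

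**After Week 45 the maximum depends on the later row.**
- SAP copy, panel at Week 73: (505 − 309)/7 = 28 weeks, then (645 − 505)/7 = 20
- That panel at Week 69 instead: (477 − 309)/7 = 24 weeks, then (645 − 477)/7 = 24
- Protocol Table 5 as it reads in the extracted text, with no panel between Weeks 45 and 93: (645 − 309)/7 = 48 weeks. This figure is uncertain and is not relied on.

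**Is the blank at EOT/EOS real?** Columns in Table 5 and SAP 14.2 shifted in extraction. Counted strictly, the two puncture marks fall at EOT/EOS and Safety Follow-up, which contradicts section 6.4; they belong at Week 97 and EOT/EOS. In both copies the last coagulation mark is one column before the first puncture mark. That is Week 93 after realignment, or Week 97 on the strict count. Neither reading puts it at EOT/EOS.

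**Is Week 21/45 right?** Some Table 4 rows also shifted by a column, but the footnote tying the panel to the preceding visit supports Weeks 21 and 45. Had the row slipped, with the panels really at Weeks 25 and 49, the gap at scheduled punctures would be 0 and the maxima (169 − 1 + 42)/7 = 30 and (337 − 169)/7 = 24 weeks. The contrast would not shrink.

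**The case against.** The strongest reply is that section 6.4 offers EOT/EOS as an alternative to Week 97, so that puncture is a moved one and the footnote already requires a panel. Visits are 4 weeks apart, a scheduled visit may stand in for EOT or EOS, and prompt timing does not forbid waiting for a result. This works when the stop is foreseen a visit ahead. When it is not, the footnote points to a visit already past.

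Other safeguards exist. Anticoagulants are prohibited throughout, medication review and hematology with platelets are scheduled at EOT/EOS, unscheduled tests are allowed, and the investigator is responsible for safety decisions. A newly started anticoagulant is more likely to be caught by medication review than by any panel, and a 4-week-old panel could miss it too. All of that stands and lowers the risk. But platelets do not replace PT/INR/aPTT, none of these checks is a stated condition for the puncture, and permission to test is not a requirement. Protocol 6.5.9 sends tests to a central laboratory except urine pregnancy and emergency tests, so a same-day result is not clearly provided for.

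The ages quoted are also worst cases. If stops were spread evenly over Weeks 21 to 45 (an assumption), the mean panel age would be 24/2 = 12 weeks, still three times the scheduled interval. Finally, the separate CSF manual might hold a pre-puncture check. Section 6.4 describes it as covering collection, processing, storage and shipment; if it does contain such a check, the protocol should refer to it.

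**Conclusion.** The concern holds and should be fixed. Followed exactly, the schedule permits a puncture at an early stop on a coagulation panel up to 26 weeks old (stops before Week 21) or 24 weeks old (stops between Weeks 21 and 45), against 4 weeks at scheduled post-baseline punctures.

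This rests on no coagulation mark at EOT/EOS, which every reading of the two shifted tables supports, and on panels at Weeks 21 and 45, which the footnote supports. Ages for stops after Week 45 are less certain.

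Only early Part 1 stoppers who have a puncture at EOT/EOS are affected. Someone who stops drug but stays on may have it at Week 97 instead, if 6.4 is read as offering one or the other. The SAP reports high attrition (sections 2 and 12) but not how many leavers had this puncture, so no rate is claimed.

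**What to change.** - Add a coagulation mark to the EOT/EOS column of protocol Table 5 and SAP 14.2.
- Extend the footnote from moved punctures to any puncture at EOT/EOS.
- Require PT/INR/aPTT and platelet results, with a local laboratory allowed, and an anticoagulant check to be reviewed before that puncture.
- Defer or omit the CSF sample if a contraindication named in exclusion 14 is present.

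Panel age at this puncture then falls to about 0 weeks. The cost is one blood tube plus local testing or a short wait for the central result. A few EOT/EOS CSF samples would be delayed, possibly with a return visit for the participant and study partner, or lost. The other EOT/EOS assessments can go ahead as planned.
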